#### 1.0 INTRODUCTION

#### 1.1 Metastatic Renal Cell Carcinoma

The estimated incidence of cancers of the kidney and renal pelvis in the United States is approximately 65,000 new cases in 2013, resulting in 13,680 deaths [1]. Renal cell carcinoma has historically presented physicians with many challenges. The often asymptomatic and clinically occult course of RCC has made it a difficult malignancy to diagnose resulting in a large proportion of patients being diagnosed with advanced or metastatic renal cell carcinoma (mRCC) [2]. In addition, prior studies have shown mRCC to be one of the most treatment-resistant solid tumors in oncology. Cytoreductive surgery and cytotoxic chemotherapy have shown limited effectiveness [3-5]. Immunotherapy has had better results, although response rates are still low and treatment is highly toxic [6-11]. The VHL-HIF pathway is pivotal to the pathobiology of RCC, and has been crucial in the development of targeted agents that include VEGFR inhibitors as well as antibodies to circulating VEGF. Furthermore, mammalian target of rapamycin (mTOR) molecules that are downstream of phosphoinositide 3-kinase and protein kinase B pathways have also demonstrated an increased concentration of HIF-alpha; thus, playing a significant role in angiogenesis [12]. Thus, the therapeutic landscape of mRCC has changed dramatically since 2005, with significant increases in overall survival [13]. This has subsequently resulted in the establishment of these agents as a first-line standard for patients with mRCC [14]. Despite their efficacy, these agents continue to be the focus of ongoing investigation, attempting to identify the best therapeutic regimen to maximize response and minimize toxicity.

# 1.2 Balancing toxicity with efficacy

Sunitinib, an oral inhibitor of vascular endothelial growth factor receptor (VEGFR) 1, 2, 3 and platelet derived growth factor receptor (PDGFR), has demonstrated prolongation of median progression free survival (PFS) in a large phase III study of patients with mRCC [6]. This led to FDA approval in 2006 and sunitinib has become a standard of care in front line treatment of mRCC.

There is emerging evidence that supports the association of relative dose intensity (RDI) of antiangiogenic agents with improvement in response rates and treatment efficacy [15, 16]. Houk et al. conducted a retrospective pharmacologic analysis across six trials of sunitinib, and determined that patients with the highest drug exposure experience longer overall survival, longer time to progression, and greater tumor reduction [15]. As can be expected, tentative relationships were also identified between total drug exposure and the incidence of fatigue, reduction in neutrophil counts and diastolic hypertension.

While the therapeutic goal in the treatment of mRCC is prolongation of survival, it is important to keep treatment related toxicities to a minimum. In real-world practice, maintenance of dose intensity of sunitinib can be challenging due to treatment-related adverse effects, including fatigue, hypertension, hand-foot syndrome (HFS) and diarrhea. In the original phase III trial, for instance, 38% and 32% of patients in the sunitinib arm underwent dose interruptions and reductions respectively, secondary to toxicities [6]. The impact of treatment related toxicities on patients can be significant, and for some patients, living longer may not always equate with living better. Wong et al. offered an interesting

insight into this, by quantifying preferences in patients with RCC who completed a survey with hypothetical treatment choice questions [17]. Their study revealed that fatigue and diarrhea were the most troublesome toxicities for patients, and that to reduce severe fatigue to mild-to-moderate fatigue, patients would be willing to forego 4.4 months of PFS. Interestingly, at the standard schedule of treatment for 4 weeks followed by a 2 week break (schedule 4/2), a cyclic scoring pattern is observed in patient reported quality of life indicators; with improvement in mean scores after the 2 week treatment break (i.e., between day 28 and day 42 scores) [18].

More recently, patient preferences for sunitinib versus active comparators were evaluated in randomized trials, results of which were presented at ESMO 2012. Data from the double blind cross-over PISCES trial comparing patient preferences between sunitinib and pazopanib, revealed that patient reported functional assessments of quality of life favored pazopanib over sunitinib with respect to fatigue, soreness of hands, feet and mouth [19]. Additionally, the phase III randomized COMPARZ study also highlighted differences in quality of life domains, which favored pazopanib over sunitinib [20]. Individual toxicities reported from this study are depicted in section 1.5. Thus, optimization of sunitinib administration is needed to maintain daily dose but to decrease the incidence of troublesome toxicity.

#### 1.3 Sunitinib

#### 1.3.1 Molecular formula and chemical name

Sunitinib is a small molecule with the molecular formula C22H27FN4O2. The free base has a molecular weight of 398.48 and the L-malate salt has a molecular weight of 532.57. The chemical name of the L-malate salt is 5-(5-fluoro-2-oxo-1,2-dihydro-indol-3-ylidenemethyl)-2,4-dimethylpyrrole-3-carboxylic acid (2-diethylamino-ethyl)-amide compound with (S)-2-hydroxy-succinic acid 1:1.

#### 1.3.2 Preclinical Data

Sunitinib is a potent inhibitor of the tyrosine kinase activity of the split-kinase domain receptor tyrosine kinases (RTKs) VEGFR2 and PDGFR, which are involved in angiogenesis, as well as for the RTKs, KIT, a receptor for stem cell factor (SCF), and FLT3 that are involved in certain solid tumors and hematological malignancies [21-24]. Sunitinib inhibits the ligand-dependent tyrosine phosphorylation of target RTKs and the in vitro mitogenic response of human umbilical vein endothelial cells (HUVECs) stimulated with VEGF or FGF, of PDGFR-expressing NIH-3T3 cells stimulated with PDGF, and of MO7E acute myeloid leukemia cells stimulated with SCF. In subcutaneous (SC) xenograft tumor models, oral administration of sunitinib results in potent inhibition of tumor growth, causing regression or stasis of large established tumors of multiple origins. The antitumor activity of sunitinib is associated with its ability to reduce tumor microvessel density in established tumors thereby acting as an inhibitor of tumor angiogenesis. Sunitinib also inhibits the growth of tumor metastases as indicated by its ability to inhibit lung colonization with B16-F1 tumor cells injected into the tail vein of athymic mice.

#### 1.3.3 Animal studies

See the Investigator's Brochure for full details. In summary, the toxicology and toxicokinetic data from studies in monkeys indicated that sunitinib treatment for up to 4 weeks with a 2-week treatment rest period (repeated cycles) was well tolerated at the dose level of 6 mg/kg/day without progression in lesion incidence and severity in the second cycle. Accumulation of sunitinib or its active metabolite was not observed in the cycling regimen indicating that plasma steady state was attained within 28 days of dosing. Similar plasma and tissue exposure is anticipated following repeated cycles of dosing. Through routine clinical monitoring, sunitinib-related adverse outcomes in animals were easily identifiable and reversible and were thus believed to be readily manageable in humans.

#### 1.3.4 Clinical Data

The clinical safety and efficacy of sunitinib has been studied in 15 phase 1 and 2 clinical trials. Dose escalation phase 1 studies were designed to determine the primary dose-limiting toxicity and maximum tolerated dose for sunitinib. Studies have also been designed to determine a safe and effective treatment schedule for repeated dosing. On all treatment schedules, patients without evidence of unacceptable toxicity or disease progression after the first cycle of treatment were permitted to receive continuing cycles of treatment until they experienced unacceptable toxicity or disease progression.

#### 1.3.5 Pharmacokinetics

The results of both single-dose and multiple-dose studies have demonstrated the favorable pharmacokinetic properties of sunitinib [25]. The Cmax and AUC appear to have increased in a proportional manner with an increase in dose after single doses of 50 to 350 mg as well as after multiple doses of 25 to 100 mg. The elimination half-life of sunitinib and its active metabolite, SU012662, are approximately 40 hours and 80 hours, respectively. Consistent with the linear pharmacokinetics of sunitinib and its active metabolite SU012662, their steady state dose-corrected plasma exposures were similar between 4/2 schedule and continuous daily dosage (CDD) schedule. The time to achievement of steady state with daily dosing of sunitinib has been assessed using trough concentrations of sunitinib, SU012662, and total drug measured during multiple dosing. These data indicate that steady-state conditions were achieved by approximately Day 10 to 14 for sunitinib. For SU012662 and total drug, steady-state conditions were achieved by Day 14 and Day 10, respectively. These findings are consistent with the half-life of sunitinib and SU012662.

Sunitinib and SU012662 concentrations measured through 3 cycles of therapy have shown that the Cmax, AUC 0-24 hr, and trough plasma drug concentrations (Cmin) during Cycle 2 or Cycle 3 were not increased above those observed in Cycle 1. Therefore, increases in plasma drug concentration would not be expected during subsequent cycles of therapy. Food does not have a significant effect on the bioavailability of sunitinib, and thus sunitinib may be administered without regard to meals. Sunitinib is metabolized primarily by the cytochrome P450 enzyme, CYP3A4, producing the active metabolite, SU012662 which is also metabolized by CYP3A4. No other major metabolite has been identified. Accumulation with multiple doses of sunitinib has been noted but is consistent with the prolonged half-lives of sunitinib (~40 hours) and its active metabolite, SU012662 (~80 hours). Chronic accumulation has not been observed across dosing intervals.

# 1.3.6 Clinical Safety

The primary DLT in the phase 1 studies appeared to be fatigue/asthenia, which generally occurred 10 to 15 days after start of therapy, and was readily reversible upon discontinuation of sunitinib malate treatment. Fatigue appeared to increase in frequency with an increase in drug exposure. The maximum tolerated dose has been defined as 50 mg in phase 1 clinical studies in subjects with advanced solid tumors, subjects with AML, and subjects with imatinib mesylate-resistant GIST.

The most serious treatment-related adverse events associated with sunitinib malate treatment of solid tumor subjects were pulmonary embolism (1.1%), thrombocytopenia (1.1%), tumor hemorrhage (0.9%), febrile neutropenia (0.4%), and hypertension (0.4%). The most common treatment-related adverse events (experienced by at least 20% of the subjects) of any grade included fatigue (48.7%); gastrointestinal disorders, such as diarrhea (39.1%), nausea (35.6%), stomatitis (27.1%), dyspepsia (24.0%), and vomiting (22.2%); skin discoloration (29.3%); dysgeusia (27.8%); and anorexia (21.6%). The maximum severity of any of these adverse events was assessed as Grade 3. Fatigue (8.2%), hypertension (5.8%) and neutropenia (5.8%) were the most common treatment-related adverse events of Grade 3 maximum severity and lipase increase (1.8%) was the most frequently occurring treatment-related adverse event of Grade 4 maximum severity in subjects with solid tumors. The degree of adverse event severity appears to correlate with higher drug exposure and/or lower subject performance status. Most patients who experienced dose limiting toxicities (DLTs) in phase I studies were noted to have combined trough plasma concentrations of sunitinib and SU012662,  $\geq 100$  ng/ml [26].

Decreases in left ventricular ejection fraction (LVEF) of  $\geq$  20% and to below the lower limit of normal occurred in subjects receiving both sunitinib malate and placebo. The LVEF declines do not appear to have a cumulative effect with repeated dosing or permanent effect since they often improved with temporary discontinuation of treatment and may not recur with reintroduction of sunitinib malate. At doses higher than the recommended human dose (RHD), sunitinib has the potential to inhibit the cardiac action potential repolarization process (e.g. prolongation of QT interval). The clinical relevance of these findings is unknown as no clinically significant QTc prolongation has been observed in completed clinical studies.

# 1.3.7 Efficacy Results

Two phase II trials of sunitinib in cytokine-refractory, metastatic RCC have been conducted [27, 28]. Both trials enrolled cytokine-refractory, metastatic RCC patients with measurable disease. Sunitinib was administered as 50 mg daily for the first 4 weeks of repeated 6-week cycles. The first trial included all histologic subtypes and demonstrated an objective partial response in 25 of 63 total patients (objective response rate 40%). The second trial restricted eligibility to clear cell RCC and required both prior nephrectomy and RECIST-defined progression after prior cytokine therapy. This trial of 106 patients reported 1 complete and 40 partial responses (objective response rate 39%, much higher than previously reported for conventional cytokine based therapy for metastatic RCC).

The success seen in the phase II trials led to a subsequent phase III trial comparing sunitinib (50 mg daily for four weeks, followed by two weeks off) to interferon-alpha (INFa) (9 million units three times per week) in previously untreated patients with metastatic clear cell RCC [6]. Overall, a significantly better objective response rate (39% vs. 8%) and median progression-free survival (11 months vs. 5 months, hazard ratio 0.54) were determined. The final analysis of the trial showed that overall survival (OS) was prolonged with sunitinib (median 26.4 versus 21.8 months, hazard ratio 0.82, 95% CI 0.67-1.00, p=0.051) [29] although the OS analysis was complicated as almost half the patients were given a VEGF inhibitor post progression (either as treatment after progressing on IFNa or as a second-line therapy after progression on sunitinib). Regardless, subsequent multivariate analysis of survival showed that initial treatment with sunitinib was a statistically significant predictor of prolonged survival, further demonstrating its efficacy in the first line setting.

#### 1.4 Rationale

Alternate schedules: While early preclinical studies intended to administer a continuous dose of sunitinib, eventually, the current 4 weeks on followed by 2 weeks off (schedule 4/2) was chosen for clinical drug development to allow for recovery from bone marrow and adrenal toxicities that were observed in animal models [26]. Thus, the standard schedule (SS) of sunitinib (50 mg once a day for four weeks followed by a 2 week treatment break; 4/2) was tested in phase I studies and demonstrated clinical efficacy with acceptable toxicities.

In clinical practice, it is often noted that adverse effects increase throughout each cycle, and tend to be worst in the final two weeks of the treatment cycle. Alternative schedules of sunitinib have been explored in clinical studies with the goal of improving drug tolerance and delivered dose intensity. A recent phase II study comparing a 37.5 mg continuous daily dose (CDD) regimen to schedule 4/2 demonstrated no differences in drug tolerance or patient reported symptoms, but established superiority of schedule 4/2 over CDD in time to tumor progression [18]. These data support the notion that higher intermittent dosing is clinically superior to lower dose, continuous administration.

An alternative dosing schema that has been used is 2 weeks on / 1 week off (schedule 2/1), in an effort to decrease adverse effects while continuing treatment. The Cleveland Clinic experience of 30 patients on the 2/1 schedule has revealed a significant improvement in drug tolerance, with no grade 4 toxicities observed on the 2/1 schedule, with less than 30% of patients experiencing grade 3 toxicity [30]. In addition, 73% of patients' worst toxicity on the 2/1 schedule was less severe than on the 4/2 schedule, and no patient's worst toxicity on the 2/1 schedule was greater than that on the 4/2 schedule (p<.0001). Fatigue and hand-foot syndrome, two of the most common toxicities, were significantly less severe on the 2/1 schedule than on the 4/2 schedule (p<.0003 in both cases). Median overall treatment duration of these patients initially on the 4/2 and, subsequently on the 2/1 schedule was 12.6 months and 11.9 months respectively. Median progression free survival (PFS) was approximately 12.7 months. These data suggest that patients with dose limiting toxicities on the 4/2 schedule are able to continue sunitinib treatment on a 2/1 schedule.

Neri et al. prospectively evaluated maintenance of dose intensity and drug tolerance in 31 patients treated with schedule 2/1, 10 of whom had previously been on the standard schedule (SS). The incidence of  $\geq$  grade 3 fatigue and HFS in this study were 16.1% and 0% respectively [31]. Table 1 depicts a comparison of reported toxicities from schedule 4/2 reported in clinical trials of sunitinib.

MD Anderson Cancer Center evaluated one hundred eighty five patients treated with frontline sunitinib for clinical outcome and toxicity as a function of treatment schedule. Eighty- seven percent started out receiving sunitinib on a conventional 4/2 schedule. During treatment, 53% of patients continued on a conventional treatment schedule and 47% initiated or transitioned to an alternate schedule, which mainly consisted of treatment with sunitinib two weeks on and one week off. Baseline characteristics were similar. Adverse effects prompting schedule modification included fatigue (64%), hand-foot syndrome (38%) and diarrhea (32%). Median time to schedule change was 5.6 months. Median overall survival (OS) was 17.7 months (95% CI = 10.8 to 22.2 months) on conventional schedule compared to 33.0 months (95% CI = 29.3 to not estimable) on an alternate schedule (P < 0.0001). By multivariable analysis; poor ECOG PS, increased LDH, decreased albumin, unfavorable Heng criteria, and conventional schedule were associated with decreased OS (P < 0.05). [32, and unpublished data]. Comparison of toxicity prevalence before and after schedule adjustment demonstrated a clear reduction in toxicity rates Table 2.

Moreover, dynamic microbubble ultrasounds (DCE-US) in patients receiving sunitinib has demonstrated reduction of tumor blood volume at day 7 and day 14, compared to baseline, with no further reduction in blood flow from day 14-28 [33]. These findings suggest that the putative anti-tumor mechanism of sunitinib, i.e. reduction in tumor-associated blood flow, is optimized after 14 days, and dosing of sunitinib from day 15-28 may increase toxicity without meaningfully contributing to efficacy. Taken together, these data provide further impetus to explore modified schedules of sunitinib. We hypothesize that sunitinib administered on a 2/1 schedule leads to a reduced incidence of ≥ grade 3 fatigue, hand-foot syndrome and diarrhea when compared to historical data, while maintaining clinical efficacy.

Table 1: Comparison of the incidence of selective toxicities of VEGFR inhibitors in metastatic renal cell carcinoma

		Fat	igue	Н	FS	Dia	rrhea	Low 1	Platelets
	No. of patient	All grade	Grade 3+	All grade	Grade 3+	All grade	Grade 3+	All grade	Grade 3+
	S			Suniti	nib				
Phase III vs. IFN 	375	54%	11%	29%	9%	61%	9%	68%	9%
EFFECT 	146	65%	9%	32%	10%	59%	6%	75%	13%
COMPARZ 	548	63%	7%	50%	12%	57%	8%	34%	16%
CCF 2/1 	30	54%	7%	17%	0%	36%	3%	7%	0%
MDACC*	-	62%	-	32%	-	32%	-	3%	-

before modification									
MDACC*	-	19%	-	2%	-	2%	-	0%	-
after									
modification									
				Pazopa	anib				
Phase III 	290	19%	2%	<10%	<1%	52%	4%	32%	1%
	554	55%	11%	29%	6%	63%	9%	10%	3%
COMPARZ 									
				Tivoza	nib				
Phase III 	259	19%	3%	13%	2%	18%	2%	17%	1%

\*unpublished data

Table 2: Prevalence of toxicity before and after schedule modification

(MD Anderson Cancer Center data)

Adverse Event	Before schedule modification N = (%)	At first follow up after schedule modification $N = (\%)$
Fatigue	40 (64)	18 (29)
Hand foot syndrome	24 (38)	6 (10)
Diarrhea	20 (32)	4 (6)
Mucositis	14 (22)	3 (5)
Nausea/vomiting	9 (14)	7 (11)
Dysgeusia	6 (10)	0
Rash	6 (10)	0
Hypertension	6 (10)	3 (5)
Anorexia	5 (8)	1 (1.5)
Mouth sores	3 (5)	0
Laboratory Abnormalities	1	
ANC < 1K/uL	3 (5)	1 (1.5)
Platelet count < 100 K/uL	2 (3)	1 (1.5)
TSH level > 4.20 IU/mL	2 (3)	0

# 2.0 OBJECTIVES

# 2.1 Primary Objective

To assess the incidence of  $\geq$  grade 3 treatment-related fatigue, hand-foot syndrome and/or diarrhea in metastatic renal cell carcinoma (mRCC) patients receiving sunitinib on a 2 weeks on / 1 week off schedule (schedule 2/1).

[figure not shown]
# 2.2 Secondary Objective(s)

- To assess the progression-free survival (PFS) of schedule 2/1 in patients with metastatic RCC.
- To assess the incidence of all  $\geq$  grade 3 toxicities on schedule 2/1
- To assess the incidence of dose reductions, dose interruptions, dose delays and rate of discontinuation for toxicity in patients with mRCC receiving sunitinib schedule 2/1.
- To assess patient reported outcomes
- To assess biologic correlatives by measuring circulating DNA levels
- To assess correlation of tumor associated macrophages with response to therapy

#### 3.0 STUDY DESIGN

# 3.1 Study schema

This is a single arm phase II study of sunitinib administered to treatment-naïve patients with clear cell mRCC. Patients will be treated with sunitinib at a starting dose of 50mg 2/1 with schedule/dose modifications for toxicity and treated until RECIST-defined progressive disease or unacceptable toxicity. Adverse events will be graded and categorized using CTCAE version 4.03 criteria. Staging studies will be assessed per RECIST v 1.

Sunitinib starting dose 50 mg by mouth daily given for 2 weeks "on" followed by 1 week "off" 1 cycle=6 weeks

# 3.2 Study Calendar

	Screening a	C1D1 (week 1)	Odd Cycles, D42 (up to Cycle 11)	Even Cycles, D42 (up to Cycle 12)	Cycles Beyond C12 h	End of Treatment	End of study
Informed consent	X						
History, physical exam and weight	X	X	X	X	X	X	X
Vital signs b	Х	X	X	X	Х	X	X
Toxicity assessment b and concomitant medications	х	Х	Х	Х	Х	Х	Х
CBC differential, platelet c	X	Xc	X	X	Х	X	Х
Serum chemistry c	Х	Xc	Х	Х	Х	Х	Х
TSH d	Х			Х	Х	Х	
LDH	Х						
B-HCG for women of child-bearing age	Х						
CT or MRI brain e	X						
CT chest/ abdomen/pelvis f (with contrast)	Х			Х	Х		Xi
Bone scan e	Х						
FACT-G QOL 		Х		Х			
Serum, plasma & buffy coat samples for biological correlates j		Х		Х	Х	Х	

One Cycle= 42 days (6 weeks).

For each visit, the following variations in time are acceptable:

A window of ± 5 days is allowed for labs and follow-up visits (except C1D1); ±7 days is allowed for restaging scans. Patients are to record blood pressure measurements in BP log daily for the first week and at least once per week thereafter. Daily intake of sunitinib should be recorded in the pill diary throughout treatment. Both will be collected during office visits by provider.

only if clinically indicated. MRI brain in lieu of CT brain acceptable.

<sup>aScreening studies must be completed within 28 days prior to administration of protocol therapy. Height to be collected at screening.

<sup>bVital signs to include temperature, blood pressure and pulse

Toxicity assessment using CTCAE v 4.03

<sup>C CBC, to be performed with differential and platelet count; Serum Chemistry to include albumin, alkaline phosphatase, total bilirubin, bicarbonate, BUN, calcium, chloride, creatinine, glucose, potassium, total protein, SGOT [AST], SGPT [ALT], sodium. **CBC/chemistry does not need to be repeated at C1D1 if previous test was within last 14 days** dThyroid function studies (TSH) should be performed every other cycle or more frequently if clinically indicated eBone scan and CT brain should be performed during screening. Subsequently, repeat scans to be performed

<sup>fCT chest/abdomen/pelvis to be repeated every 2 cycles

<sup>9FACT-G to be administered at visits during baseline, week 12, week 24 and week 36 assessments prior to MD encounter. Study team to check for completion of QOL data: more than 50% questions in each subscale, and at least 80% of questions overall in each questionnaire should be answered for the questionnaire to be considered complete.

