#### 4.2 Exclusion Criteria

The presence of any of the following will exclude a patient from study enrollment.

- 1. Prior treatment with sunitinib or any other systemic therapy in the metastatic setting (prior neo/adjuvant therapy will be allowed if completed > 6 months prior to registration and therapy not discontinued for toxicity)
- 2. Uncontrolled hypertension (defined as blood pressure >140/90 mm Hg not controlled with anti-hypertensives)
- 3. Prior intraabdominal, intrathoracic, vascular, spinal or intracranial surgery or radiation therapy within 4 weeks of starting treatment
- 4. History of or known brain metastases, spinal cord compression, or carcinomatous meningitis
- 5. New York Heart Association (NYHA) grade II or greater congestive heart failure
- 6. Current treatment on another therapeutic clinical trial

<sup>h Labs and follow-up visits can be every 12 weeks after completion of 12 cycles, at the discretion of the treating physician

<sup>iEOS visit does not require CT scans if performed within the preceding 12 weeks.

<sup>1Biological correlates to include characterization of circulating DNA and tumor associated macrophages.

- 7. Any of the following within the preceding 6 months- myocardial infarction, severe/unstable angina, severe peripheral vascular disease (claudication) or procedure on peripheral vasculature, coronary/peripheral artery bypass, graft, cerebrovascular accident or transient ischemic attack, clinically significant bleeding
- 8. Pregnant or breastfeeding women are excluded from this study because there is an unknown, but potential risk for adverse events in nursing infants secondary to treatment of the mother with sunitinib. Breastfeeding must be discontinued if the mother is treated with sunitinib
- 9. Known human immunodeficiency virus (HIV) or acquired immunodeficiency syndrome (AIDS)-related illness
- 10. HIV-positive patients on combination antiretroviral therapy are ineligible because of the potential for pharmacokinetic interactions with sunitinib. In addition, these patients are at increased risk of lethal infections when treated with marrow suppressive therapy

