# 6.3 Duration of Therapy

In the absence of treatment delays due to adverse events, treatment may continue indefinitely until one of the following criteria applies:

- Disease progression per RECIST version 1.
- The investigator considers it, for safety reasons, to be in the best interest of the patient.
- Unacceptable adverse event(s) related to treatment, defined as a grade 3 or 4 toxicity (per CTCAE v 4.03) that fails to recover to < Grade 2 in the absence of treatment within 4 weeks
- General or specific changes in the patient's condition render the patient unacceptable for further treatment in the judgment of the investigator
- Patient decision to withdraw from treatment (partial consent) or from the study (full consent)
- Pregnancy during the course of the study for a child-bearing participant

The date and reason for discontinuation must be documented. Every effort should be made to complete the appropriate assessments.

If in the opinion of the investigator, the patient demonstrates disease progression by RECIST, but the patient is demonstrating obvious clinical benefit to sunitinib therapy, the investigator may choose to continue patient on study. At the time that clinical benefit from study drug is no longer apparent, investigator will take patient off study and off study drug.

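### Beta-HCG is scheduled once, at screening up to 28 days before first dose, with no pre-dose recency rule and no scheduled repeat during open-ended treatment

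*Combined protocol and SAP*

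**What the plan says.** **Entry.** Section 4.2, item 8: "Pregnant or breastfeeding women are excluded from this study".

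**Stopping.** Section 6.3 says "treatment may continue indefinitely until one of the following criteria applies", and one of those criteria is "Pregnancy during the course of the study for a child-bearing participant".

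**Testing.** In the Study Calendar (3.2) the row "B-HCG for women of child-bearing age" is marked in the screening column and nowhere else. Footnote a sets the timing: "Screening studies must be completed within 28 days prior to administration of protocol therapy". Section 12.1 lists the test among the screening laboratory studies. Section 12.2 does not list it at cycle 1 day 1, at day 42 of cycle 1, cycle 2 or later cycles, at end of treatment, or at the 30-day follow-up.

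**Other blood tests.** The blood count and chemistry panel have a recency rule before first dose: "CBC/chemistry does not need to be repeated at C1D1 if previous test was within last 14 days". Both are repeated at every day-42 visit, and TSH is repeated in even-numbered cycles.

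**The concern.** The protocol makes pregnancy a reason to stop sunitinib but schedules no test that would reveal one during treatment. A woman who conceives after the screening draw can be dosed, and can go on being dosed, with the schedule followed exactly. Detection then rests on her own report or on clinical suspicion at a visit. The protocol itself counts a congenital anomaly or birth defect as a serious outcome (8.2.2). Beta-HCG checks an exclusion and bears on a stopping rule, yet it has neither the pre-dose recency rule nor the repeats given to routine blood tests.

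**Working it through.** No design figure in the plan depends on this point, so there is none to reproduce. The check is a comparison of visit lists, followed by interval arithmetic.

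**Step 1: where the test is scheduled.**

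| Visit | Calendar (3.2) | Section 12 |
|---|---|---|
| Screening | marked | listed (12.1) |
| Cycle 1 day 1 | no | no |
| Day-42 visits, odd and even cycles | no | no |
| Beyond cycle 12 | no | no |
| End of treatment | no | no |
| End of study, 30 days | no | no |

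The calendar was read from a PDF and its columns could have shifted, but the visit lists in section 12 give the same result independently.

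**Step 2: the schedule as written.** Inputs: 28-day screening window (3.2, footnote a); 42-day cycle (3.2); expected median PFS of 11 months (16.5), used here only as an assumed time on treatment.

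- Age of result at first dose: up to 28 days.
- Scheduled on-treatment tests: 0. From scheduled test to scheduled test, the interval therefore has no upper limit.
- Illustration: 11 × 365.25 / 12 = 334.8 days, and 334.8 / 42 = 7.97, or about 8 cycles without a scheduled test. Measured from the screening draw, the time is up to 334.8 + 28 = 362.8, about 363 days.

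**Step 3: with a 14-day limit before first dose and a test at each day-42 visit.** If first dose is day 1, day 42 is 41 days later; counting a full cycle gives 42. Visit windows are ±5 days, with none at cycle 1 day 1 (3.2).

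| Interval | Formula | Days | With windows |
|---|---|---|---|
| Last pre-dose test to cycle 1 day 42 | 14 + 41 to 14 + 42 | 55-56 | 60-61 (+5) |
| The same with a 7-day limit | 7 + 41 to 7 + 42 | 48-49 | 53-54 (+5) |
| Day 42 to next day 42 | 42 | 42 | 52 (+10) |
| 12-weekly visits after cycle 12 | 12 × 7 | 84 | 94 (+10) |

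Dosing is in weeks 1, 2, 4 and 5 (6.1), so a woman would have 4 × 7 = 28 dosing days before the first on-treatment test (33 if that visit is 5 days late).

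**Step 4: added assays per woman.** Over 11 months there are 7 complete cycles, and the eighth day-42 visit falls due on about day 336, so 7-8 visits. Add 0-1 pre-dose repeat and 1 at end of treatment: 7 + 0 + 1 = 8 to 8 + 1 + 1 = 10.

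Range for other assumed durations:

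- 6 months: 182.6 / 42 = 4.3, so 4 visits and 5-6 assays.
- 16 months: 487 / 42 = 11.6, so 11 visits and 12-13 assays.

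The documents do not say how many of the 60 will be women of child-bearing potential, so no trial total can be given.

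**The case against.** The case for leaving the schedule alone is that no protocol rule is broken. The 28-day window applies to the other screening tests too, and exclusion 8 governs entry, for which the screening test is the check. Section 6.3 does not tie the stopping rule to a test, and several of its other criteria also rest on report or judgement. History, examination and toxicity assessment are scheduled at every visit. The 14-day limit is borrowed from the blood-count rule for convenience and has no basis in pregnancy detection. The fix would still leave gaps.

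Most of this stands, and it limits what may be claimed. A reader might infer any of the following, none of which the documents support:

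- **The protocol contradicts itself, or exclusion 8 is not enforced.** The screening test does check entry. What is left open is the time between the draw and first dose, and then the stopping rule during treatment.
- **Pregnancy testing is ruled out after screening.** It is only unscheduled; nothing bars a test when pregnancy is suspected.
- **The trial has no pregnancy or contraception provisions.** The consent pages were removed and Appendix D was not among the documents available. Either could contain such wording, even repeat testing. The point is confined to the calendar and section 12.
- **The pelvic CT is the present safeguard, so the interval to it measures the gap.** Footnote f says "CT chest/abdomen/pelvis to be repeated every 2 cycles", but this is restaging. Setting a test-to-scan interval beside a test-to-test interval would not compare like with like.

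The objection does not answer the main point. With the schedule followed exactly, pregnancy during open-ended treatment is found only by report or suspicion, although blood is already drawn at the visits where an assay could be added.

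**Conclusion.** The point holds as a gap in the schedule that is cheap to close. As written, the result may be 28 days old at first dose and the scheduled on-treatment interval is unbounded. With the change, the longest scheduled interval is 55-56 days at first, 42 days through cycle 12, and 84 days if visits become 12-weekly, before windows. Undetected exposure is limited but not removed.

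The 8-cycle illustration and the assay counts assume that time on treatment is about the expected median PFS; toxicity may shorten it, and 6.3 allows treatment beyond progression where there is clinical benefit. The number of women affected is unknown and may be small, so no expected number of exposures can be stated. The matter concerns participant safety only. It does not alter the composite toxicity endpoint, the sample size of 60 or the rule that the upper confidence limit be below 25%.

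**What to change.** Amend the Study Calendar (3.2) and the visit lists in section 12, for women of child-bearing potential only:

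1. Keep the screening beta-HCG and require a negative result no older than 14 days at first dose, repeating the test only if the screening result is older. Fourteen days matches the blood-count and chemistry rule, so one draw can serve both. Seven days, matching the general cycle 1 day 1 rule in 12.2, is the stricter option.
2. Add beta-HCG to the blood already drawn at each day-42 visit and at the 12-weekly visits after cycle 12.
3. Add it to the end-of-treatment laboratory list.

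No test is proposed at the 30-day visit, because the stopping rule no longer operates once treatment has ended.

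The cost is a short amendment and about 8-10 assays per woman over an assumed 11 months, on blood drawn at existing visits apart from any pre-dose repeat. A repeat result must be back before dosing, which could delay day 1 slightly. If the consent form or Appendix D already requires repeat testing, the calendar need only be brought into line with it.
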